## **12.0**            **HEALTH OUTCOME MEASURES**

Patient ocular symptom questionnaire that assessed 7 symptoms related right, left or both eyes will be administered at screening, Months 3, 6, 12 or Study Exit visit. Seven symptoms assessed are:

- Eye irritation, burning
- Eye pain
- Excessive tearing
- Droopy eyelids
- Red eyes
- Feeling like something in your eye
- Skin sensitivity or irritation around eye

Responses will be recorded as whether a symptom occurred or not.

Number and percent of patients with each of the above symptoms occurring in the SE will be presented by visit.

Further detailed analysis of the above symptoms is not part of this SAP and will be described elsewhere by the group at Allergan that specializes in the analyzing of health outcome measures.

### **13.0 INTERIM ANALYSIS**

No interim analysis is planned for this study.

### **14.0 DETERMINATION OF SAMPLE SIZE**

Fifty patients will provide a precision of at least  $\pm 0.145$  to estimate the proportion of patients achieving an IOP reduction  $\geq 20\%$  at 12 months on the same number or fewer IOP-lowering medications compared with baseline based on a 95% exact Clopper-Pearson CI for binomial proportions. Sixty-five patients will be implanted to ensure at least 50 evaluable patients who are defined as implanted patients with 12 months of follow-up.

### **15.0 STATISTICAL SOFTWARE**

Statistical analyses will be performed using version 9.4 (or newer) of SAS software.

### **16.0 DATA HANDLING CONVENTIONS**

#### **16.1 VISIT TIME WINDOWS**

Table 16.1–1 presents the analysis visits assigned for efficacy and safety analyses and the corresponding range in Study days (window) during which an actual visit may occur.

Table 16.1–1. Visit Time Windows

Analysis Visit	Target Visit Daya	Window
Baseline	Day 1	Days $\leq 1$
Day 2	Day 2	Days [2, 4]
Day 8	Day 8	Days [5, 11]
Week 2	Day 15	Days [12, 22]
Month 1	Day 31	Days [23, 61]
Month 3	Day 92	Days [62, 137]

Month 6	Day 183	Days [138, 213]
Month 8	Day 244	Days [214, 274]
Month 10	Day 305	Days [275, 335]
Month 12	Day 366	Days $\geq$ 336

a Relative to the date of the XEN implant. Day 1 = the date of the XEN implant. There is no Day 0 or Week 0.

If an assessment date (if the assessment date is unavailable, use visit date instead) is on or after the date of XEN implant, the study day is calculated using (Assessment date – date of the XEN implant + 1). If the assessment date is before the date of the XEN implant, the study day is calculated using (Assessment date – date of XEN implant). Therefore, a negative day indicates a day prior to XEN implant date.

For multiple scheduled or unscheduled visits falling within the same analysis visit window, the assessment closest to the target visit day will be used for by visit summaries. If two visits are equally close to the target visit day, the later visit will be used as analysis visit.

For by visit and severity summaries, the results with maximum severity for the visit should be chosen if multiple scheduled or unscheduled visits falling within the same analysis visit window.

For number of IOP-lowering medications taken during post-baseline visits, analysis visits for IOP measurements will be derived first. Post-baseline analysis visit days of IOP measurements will then be compared to start and stop date of each concomitant IOP-lowering medication record to determine number of IOP-lowering medications taken during post-baseline visits.

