6.1.1 Screening Visit

The window for this visit is up to 60 days prior to surgery. After obtaining informed consent ([Section 10.1.2](#)), the following information will be obtained at this visit:

- Evaluation of inclusion/exclusion criteria
- Patient demographics
- Medical history, surgical history, ophthalmic history, and ophthalmic surgical history, including presence of ocular pathology and concomitant ocular medications (both eyes)
- Patient ocular symptom questionnaire

- Concomitant medications (systemic and ophthalmic) and procedures
- AEs
- Urine pregnancy test (for females of childbearing potential)
- Manifest refraction (both eyes)
- BCVA using LogMar chart (both eyes)
- Visual field testing (both eyes): Monocular visual field testing will be measured using the Humphrey 24-2 full threshold program or Swedish Interactive Thresholding Algorithm (SITA) Standard and a reliable, interpretable visual field will be obtained for patients with a preoperative BCVA of better than 20/100. This assessment is not required for patients with BCVA of 20/100 or worse. Visual field results must be reliable and interpretable, or if unreliable or uninterpretable, the visual field test must be repeated. An unreliable visual field is defined as visual field measurements with > 33% fixation losses, false positives, or false negatives. Visual field test performed up to 6 months prior to operative day (Day 1) is allowed.
- Biomicroscopic slit lamp examination (both eyes): includes determination of ophthalmic medical observations/complications, evaluation of the condition of the eyelids, conjunctiva, cornea, anterior chamber, iris/pupil, and lens (through a dilated pupil).
- IOP (Hour 0 = 8:00 am \pm 1 hour) measurement using Goldmann applanation tonometry (both eyes) using the 2-person reading method (See Protocol Procedure Manual); IOP must be completed prior to pachymetry, gonioscopy, and ophthalmoscopy.
- Pachymetry measurement of central corneal thickness (both eyes) using an ultrasonic pachymeter
- Gonioscopy (both eyes): includes assessment of angle abnormalities, such as peripheral anterior synechiae, angle assessment of each quadrant by Shaffer Grade

- Ophthalmoscopy (both eyes): includes dilated fundus evaluation and vertical cup-to-disc ratio. Non-dilated ophthalmoscopy may be performed if the investigator believes that pupil dilation may put the patient at risk.

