### **8.2 BASELINE AND DISEASE CHARACTERISTICS**

Following baseline characteristics will be descriptively summarized for the patients in the Implanted Population (baseline is defined in Section 16.1):

- Study eye (SE) [right (OD), left (OS)]
- Lens status of study eye (phakic, pseudophakic, aphakic)
- Number of prior IOP-lowering medications (0, 1, 2, 3, 4, 5, >5), see Section 8.4.2 for IOP-lowering medication counts.
- Screening and baseline IOP [Hour 0] of SE (mmHg) category (<20, 20-25, >25-30, >30-35, and >35 mmHg) and descriptive summary at baseline
- Best corrected visual acuity (BCVA) of the SE (20/40 or better, <20/40 to 20/100, and worse than 20/100)
- Visual field result of SE (normal, abnormal). Abnormalities will be further broken down by abnormality condition (enlargement of blind spot, superior arcuate scotoma, inferior arcuate scotoma, paracentral scotoma, nasal step, central scotoma, generalized depression, temporal scotoma, other)
- Visual field mean deviation (dB) or mean defect of the SE (+, -)
- Ophthalmoscopy, cup to disc ratio of SE at baseline
- Contact Pachymetry at screening: central corneal thickness mean (µm) of the SE, and a categorical summary (<500, 500-<525, 525-<550, 550-<575, 575-<600 and ≥600 µm)

In addition, following medical history data collected on the ‘Medical and Surgical History/Physical Findings’ eCRF page will also be summarized.

- History of trabeculectomy or glaucoma shunt implantation (yes, no)
- History of trabeculectomy (yes, no)
- History of glaucoma shunt implantation (yes, no)
- Prior Cataract Surgery (yes, no)
- Prior Glaucoma Procedure (yes, no).
  - Yes, with incisional or cilioablative procedure
  - Yes, without incisional or cilioablative procedure

A look-up table of Medical Dictionary for Regulatory Activities (MedDRA) terms to identify the following procedures will be provided by the study medical safety physician (MSP):

- Trabeculectomy
- Glaucoma shunt implantation
- Cataract Surgery
- Glaucoma Procedure
  - Incisional or cilioablative procedure
  - Not incisional or cilioablative procedure

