**Visual Field Test:** Visual field tests will be performed at baseline and at Month 12/Early Exit visits. Number and percent of patients with an abnormal visual field in SE will be presented by visit and abnormality condition (Enlargement of blind plot, Superior arcuate scotoma, Inferior arcuate scotoma, Paracentral scotoma, Nasal step, Central scotoma, Generalized depression, Temporal scotoma, or Other). Note that a patient may have more than one abnormality condition. Further, visual field mean deviation and change from baseline to Month 12/Early Term will also be descriptively summarized. A change (Month 12/Early Term – Baseline) in visual field mean deviation measured using the same program of > 3.0 dB will be categorized as ‘Better’, a change of -3.0 dB to +3.0 dB will be categorized as ‘no change’ and a change of <-3.0 dB will be categorized as ‘Worse’. Number and percent of patients belonging to each the three categories will also be presented.

**Pachymetry:** Contact pachymetry will be performed at screening and Month 12/Early exist. Three measurements of central corneal thickness and their average are recorded. These average values will be summarized by visit. Changes from screening to Month 12/Early exit visit will also be summarized.

**Gonioscopy:** Gonioscopy exams will be performed at screening, month 1, 6 and 12/Early Exit. The findings will be summarized by visit.

**Ocular Biomicroscopic Exam:** These exams will be performed at screening, baseline, Day 2, Day 8, Week 2, Months 1, 3, 6, 8, 10 and 12/Early Exit. At each of these exams, any findings related to Eyelids/Eyelid Margins/Lashes, Conjunctiva (Bulbar of

Palpebral), Cornea, Anterior Chamber, or Iris/Pupil are noted (yes, no, not evaluable) will be recorded. Number and percent of patients showing findings in each of the above areas will be summarized by visit. Further, associated with each eye, symptom severity data except for 'Iris/Pupil' will also be collected for the sub-categories described below:

- Eyelids/Eyelid Margins/Lashes:
  - Erythema
  - Edema
  - Other
- Conjunctiva:
  - Hyperemia
  - Edema
  - Subconjunctival Hemorrhage
  - Pterygium, encroaching on visual axis
  - Pterygium, not encroaching on visual axis
  - Other
- Cornea (Central, Peripheral, or Central and Peripheral):
  - Filaments
  - Infiltrates
  - Edema
  - Corneal Guttata
  - Endothelial Pigment
  - Keratic Precipitates
  - Neovascularization
  - Opacity
  - Stromal Haze
  - Other
- Anterior Chamber:

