  - Cells
  - Flare
  - Anterior Synechiae
  - Hypopyon
  - Hyphema
  - Other

Number and percent of patients in each of the above sub-categories will be presented using the worst severity observed in the SE by visit.

**Ophthalmoscopy Exam:** These exams will be performed at Screening, Baseline, Months 1, 3, 6 and 12/Early Exit. At each of these exams, any findings noted (yes, no, not

evaluable) in the ‘Vitreous’, ‘Optic Nerve Exam’, ‘Fundus Exam’, ‘Macula’, and ‘Retina Periphery’ will be recorded.

Number and percent of patients with findings noted in the above areas in the SE will be summarized by visit. Further, following data will also be collected associated with each of the above categories.

Vitreous: Severity (+0.5, +1, +2, +3, +4, not evaluable) associated with each finding: ‘Cells’, ‘Vitreous Haze’, ‘Vitreous Hemorrhage’, ‘Posterior Vitreous Detachment’ and ‘Other’. These data associated with the SE will be summarized in number and percent of patients format by visit.

Optic Nerve: ‘Disc Hemorrhage’ and ‘Other Disc Pathology’. Number and percent of patients with findings in each of these two areas in the SE will be summarized by visit.

In addition, Optic Nerve-Cup/Disc ratio data (numerical) of the SE will also be summarized by visit.

**Lens Status and Opacification**: Lens status findings questionnaire will be administered at screening, baseline, Months 1, 3, 6 and 12/Early Exit. Lens status at each assessment will be recorded as ‘Phakic’, ‘Pseudophakic’ or ‘Aphakic’. Lens status of the SE will be summarized by visit.

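### SAP 16.1 pools screening and baseline exams in one Baseline window, so the maximum-severity rule can overstate baseline in the graded slit-lamp and vitreous tables

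*SAP*

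**What the plan says.** SAP 8.2 sends the reader elsewhere for the definition of baseline: "baseline is defined in Section 16.1". Table 16.1-1 in that section has no Screening row. Its Baseline row has target Day 1 (the implant date) and takes in all days up to and including Day 1. It has no lower limit and no condition that the assessment precede implantation.

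Two rules then choose among several assessments in one window:

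- Ordinary by-visit summaries: "For multiple scheduled or unscheduled visits falling within the same analysis visit window, the assessment closest to the target visit day will be used". Ties go to the later visit.
- Tables of graded severity follow a different rule: "the results with maximum severity for the visit should be chosen if multiple scheduled or unscheduled visits falling within the same analysis visit window".

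SAP 11.3 makes the slit-lamp sub-category table a severity summary: "Number and percent of patients in each of the above sub-categories will be presented using the worst severity observed in the SE by visit". In ophthalmoscopy only the vitreous findings carry a severity grade.

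On timing, SAP 11.3 says of the slit lamp: "These exams will be performed at screening, baseline, Day 2, Day 8, Week 2, Months 1, 3, 6, 8, 10 and 12/Early Exit". Of ophthalmoscopy it says: "These exams will be performed at Screening, Baseline, Months 1, 3, 6 and 12/Early Exit". Protocol 6.1.1 says of screening: "The window for this visit is up to 60 days prior to surgery". Protocol 6.1.2 puts the baseline visit 5 to 7 days before surgery.

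**The concern.** Screening and the baseline visit both fall in the Baseline window. A programmer following Section 16.1 would pool the two exams and keep the worse grade, while a routine post-operative column rests on one exam. The worse of two exams can equal or exceed a single one but never fall below it. Among scheduled exams the comparison therefore leans one way: the eye looks worse before surgery, and new post-operative edema, cells or flare stand out less. In a single-arm study the pre-operative column is the natural reference for these tables, and the error favours the device.

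A second, contingent weakness is that the window includes the whole operative day and its target is Day 1. SAP 16.2 allows unscheduled BCVA and gonioscopy. If either were done after surgery on Day 1, it would be classed as Baseline and, being exactly on target, would displace the true pre-operative value. For BCVA this would carry into the line change from baseline in SAP 11.3.

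**Working it through.** The plan gives no figure on this point to reproduce. The check has two parts.

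**1. Scheduled exams per analysis window.** Inputs: visit windows from the schedule of visits (Protocol Table 1-1, SAP Table 4-1); target days and analysis windows from SAP Table 16.1-1.

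| Scheduled visit | Possible study days | Analysis window |
|---|---|---|
| Screening | -60 to -5 | Baseline (≤ 1) |
| Baseline | -7 to -5 | Baseline (≤ 1) |
| Day 2 | 2 | 2–4 |
| Day 8 | 6–10 | 5–11 |
| Week 2 | 12–18 | 12–22 |
| Month 1 | 26–36 | 23–61 |
| Month 3 | 82–102 | 62–137 |
| Month 6 | 169–197 | 138–213 |
| Month 8 | 230–258 | 214–274 |
| Month 10 | 291–319 | 275–335 |
| Month 12 | 352–380 | ≥ 336 |

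The Baseline window holds two scheduled exams. No two routine post-operative visits share a window.

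**2. Illustrative size.** Let p be the chance that a finding is graded present on one exam, the same at both pre-operative exams. Then

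P(present on the worse of two) = 2p − P(present on both).

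P(both) comes from a bivariate normal threshold model with latent correlation r. Neither p nor r is in the documents; both are assumptions.

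| p | r | P(both) | Shown at Baseline | Excess (points) | Excess patients of 65 |
|---|---|---|---|---|---|
| 0.10 | 0 | 0.010 | 0.200 − 0.010 = 19.0% | 9.0 | 5.9 |
| 0.10 | 0.5 | 0.032 | 0.200 − 0.032 = 16.8% | 6.8 | 4.4 |
| 0.10 | 0.8 | 0.056 | 0.200 − 0.056 = 14.4% | 4.4 | 2.8 |
| 0.20 | 0 | 0.040 | 0.400 − 0.040 = 36.0% | 16.0 | 10.4 |
| 0.20 | 0.5 | 0.087 | 0.400 − 0.087 = 31.3% | 11.3 | 7.3 |
| 0.20 | 0.8 | 0.129 | 0.400 − 0.129 = 27.1% | 7.1 | 4.6 |

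If the exams always agree, P(both) = p and the excess is 0. For a rarer finding, p = 0.02, even independence gives only 0.04 − 0.0004 = 3.96%, an excess of just under 2 points.

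The correlation scale matters. Written with the correlation ρ between the yes/no findings themselves, the excess is p(1 − p)(1 − ρ). At p = 0.10, latent 0.8 corresponds to ρ of about 0.51, and 0.10 × 0.90 × 0.49 = 0.044, the same 4.4 points. A ρ of 0.8 on the yes/no scale is much closer agreement and gives 0.10 × 0.90 × 0.20 = 1.8 points.

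Extra post-operative exams pull the other way. If a share u of patients has one additional exam in a post-operative window, with the same p and correlation, the Baseline excess over that window is multiplied by (1 − u): halved at u = 0.5, zero at u = 1.

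**The case against.** Most of the case on the other side limits the point and stands.

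- **Reach.** A reader might infer that slit-lamp and fundus findings in general are overstated. They are not. The yes/no slit-lamp findings, the ophthalmoscopy findings by area, the optic-nerve findings and the cup/disc ratio are ordinary by-visit summaries. Of the two scheduled exams, the closest-to-target rule picks the baseline visit for them.
- **Direction.** The maximum rule applies in every window and takes in unscheduled visits. Protocol 6.1 has slit-lamp and ophthalmoscopy findings from such visits reported, and an early-exit exam can share a window with a scheduled one. Overstatement is possible, not certain.
- **Size.** Independence between two exams of one eye within about 60 days is implausible for lasting findings such as guttata or synechiae. The eligibility criteria also exclude recent clinically significant inflammation, so some graded findings may be rare at baseline.
- **Operative day.** A reader might infer that surgical complications will be counted as pre-existing. The schedule has no eye examination on Day 1. Adverse events count as treatment-emergent from the start of the implant procedure (SAP 11.1), and surgical complications and post-implantation bleeding have their own summary (SAP 11.2.1). Neither depends on the visit windows.
- **Role of the tables.** SAP 11.3 specifies by-visit frequencies for these findings, with no shift or change-from-baseline severity analysis.
- **Intent.** SAP 8.2 and 11.3 name screening and baseline separately, so the missing row may be an omission.

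The last point does not remove the problem. Section 16.1 is the stated source of the definition, and followed as written it pools the two exams.

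**Conclusion.** The point holds for two descriptive displays: the graded slit-lamp sub-category table and the vitreous grades. Their Baseline column is the worse of two scheduled exams, against at most one routine scheduled exam in each post-operative window. It can be overstated and can partly mask worsening. Under the assumed inputs the excess is 4 to 9 points for a 10% finding and 7 to 16 points for a 20% finding, at latent correlation 0.8 to 0. It shrinks to nothing as the two exams agree or as extra post-operative exams accumulate.

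The Day 1 boundary is a real gap in the definition, but it matters only if an unscheduled exam is done after surgery that day. The documents do not say how often that happens.

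The maximum-severity rule does not touch the primary endpoint, and SAP 10.1.1 takes baseline Hour 0 IOP from its own eCRF page. The correction is worth making because it costs little and the uncorrected rule can favour the device.

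**What to change.** In SAP 16.1:

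1. Define Baseline for safety parameters as the last non-missing assessment before the start of the XEN procedure. A screening value then still serves where it is the only scheduled pre-operative one, as for gonioscopy, pachymetry and visual field.
2. Add a separate Screening analysis visit.
3. Assign any Day 1 assessment made after implantation to the first post-operative window.
4. State that the maximum-severity rule is not applied across screening and baseline.

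The cost is a few lines of text and the matching programming. No new data are needed beyond the assessment time or visit label for any Day 1 exam. One small downside remains: a post-operative window with unscheduled exams would show the worst of several exams against a single baseline exam. That is conservative for safety and should be footnoted in the tables.

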## **16.2 REPEATED OR UNSCHEDULED ASSESSMENTS OF SAFETY PARAMETERS**

Following unscheduled assessments are allowed: Pregnancy test, IOP assessment, Manifest refraction, Gonioscopy, Pachymetry, BCVA and Visual field exam.

IOP assessment done at unscheduled visits for safety purpose will not be included in efficacy analysis of IOP.

## **16.3 MISSING SEVERITY ASSESSMENT FOR ADVERSE EVENTS**

If severity is missing for an AE that started before the date of XEN implant, severity of mild will be assigned. If severity is missing for an AE that started on or after the date of

XEN implant, severity of 'severe' will be assigned. The imputed values for severity assessment will be used for the incidence summaries; the values will be shown as missing in the data listings.

#### **16.4 MISSING CAUSAL RELATIONSHIP TO XEN IMPLANT FOR ADVERSE EVENTS**

If the causal relationship to the study treatment is missing for an AE that started on or after the date of XEN implant, a causality of 'yes' will be assigned. The imputed values for causal relationship to study treatment will be used for the incidence summaries; the values will be shown as missing in the data listings.

#### **16.5 MISSING DATE INFORMATION FOR ADVERSE EVENTS**

Per database design, only the day part of an AE start or stop date could be set to 'unknown', month and year cannot be set to 'unknown'. If the day part is missing, it will be set to the day part of XEN implant date. However, after the imputation if the stop date appears to be before the start date, start date will be set to stop date if the stop date was complete (non-missing) and stop date will be set to start date if the start date was complete (non-missing).

#### **16.6 MISSING DATE INFORMATION FOR PRIOR OR CONCOMITANT MEDICATIONS**

For prior or concomitant medications, including medications of interest, incomplete (i.e., partly missing) start dates and/or stop dates will be imputed. Per database design, year part of a medication start or stop date cannot be set to 'unknown'. When the start date and the stop date are both incomplete for a patient, the start date will be imputed first.

##### **16.6.1 Incomplete Start Date**

The following rules will be applied to impute the missing numeric fields for an incomplete prior or concomitant medication start date. If the stop date is complete (or imputed) and the imputed start date is after the stop date, the start date will be imputed using the stop date.

##### **Missing month and day**

- If the year of the incomplete start date is the same as the year of the XEN implant date, the month and day of the XEN implant will be assigned to the missing fields

- If the year of the incomplete start date is before the year of the XEN implant date, *December 31* will be assigned to the missing fields
- If the year of the incomplete start date is after the year of the XEN implant, *January 1* will be assigned to the missing fields.

#### **Missing month only**

- If only the month is missing, the day will be treated as missing and both the month and the day will be replaced according to rules described above.

